# 6.3.2.3 Overall Summary of Primary and Secondary Endpoints in Hierarchical Testing

An overall summary table of treatment comparisons of primary and secondary endpoints tested hierarchically displays the following statistics:

- Continuous endpoints involving change from OP or baseline
  - on (i.e., number of subjects in the analysis set), LSM change, and 97.5% CI for each zavegepant treatment group and placebo pooled
  - Difference in LSM changes between each zavegepant treatment group and placebo pooled, and 97.5% CI..

This applies to the primary endpoint and the following secondary efficacy and outcomes research endpoints: mean change in number of migraine days per month in the last month of the DBT Phase (see main analysis in Section 6.3.1); mean change in number of migraine days per month in the first month of the DBT Phase (see main analysis in Section 6.3.1); MSQoL restrictive role domain score mean change from baseline at Week 12 (see Section 6.5.1); and MIDAS total score mean change from baseline at Week 12 (see Section 6.5.2).

- Continuous endpoints not involving change from OP or baseline
  - on, LSM, and 97.5% CI for each zavegepant treatment group and placebo pooled
  - Difference in LSMs between each zavegepant treatment group and placebo pooled, and 97.5% CI.

This applies to the secondary efficacy endpoint of the mean number of acute migraine-specific medication days per month over the entire DBT Phase (see Section 6.3.2.2).

- Binary endpoints
  - Response rate ("n/N" and percentage) and 97.5% CI for each zavegepant treatment group and placebo pooled
  - Stratified percentage difference between each zavegepant treatment group and placebo pooled, and 97.5% CI.

This applies to the secondary efficacy endpoint of percentage of subjects with  $\geq 50\%$  reduction in number of moderate or severe migraine days per month over the entire DBT Phase (see Section 6.3.2.1).

Endpoints are displayed in the order presented in Sections 3.2.1 and 3.2.2.

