9.1 Sample Size

With a sample size of approximately 480 randomized subjects per zavegepant treatment group and 240 randomized subjects per placebo treatment group, we expect approximately 440 subjects per zavegepant treatment group and 220 subjects per placebo treatment group in the migraine analysis set. Assuming zavegepant provides a 1-day advantage over placebo pooled on the mean change in migraine days per month over the entire DBT Phase (Weeks 1 to 12), and a common standard deviation of 4.2 days, then the study will have \geq 90% power for the primary endpoint with an alpha level of 0.025. The estimates for the migraine analysis set sample size, mean change in migraine days per month, and standard deviation are based on observed pooled data from rimegepant study BHV3000-305.

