9.3.1.3 Adjustment for Multiplicity

Type 1 error is controlled through the use of hierarchical testing. The significance of the primary endpoint is evaluated at the 0.025 level for each dose of zavegepant versus placebo. If the primary endpoint is significant for a dose, then the following secondary efficacy and outcomes research endpoints will be tested hierarchically in the following order, each at the 0.025 level:

- Proportion of subjects with ≥ 50% reduction from the Observation Phase in the number of moderate or severe migraine days per month over the entire DBT Phase
- Mean change from the Observation Phase in the number of migraine days per month in the last 4 weeks of the DBT Phase
- Mean change from the Observation Phase in the number of migraine days per month in the first 4 weeks of the DBT Phase
- Mean number of acute migraine-specific medication days per month over the entire DBT Phase
- Mean change from baseline in MSQ restrictive role function domain score at Week 12 of the DBT Phase
- Mean change from baseline in MIDAS total score at Week 12 of the DBT Phase.

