## 1.1 Research Hypothesis

Zavegepant 100 mg or zavegepant 200 mg soft gelatin capsule (SGC) oral dose taken daily is safe and effective for the prevention of migraine.

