## 5 SAMPLE SIZE, POWER, AND TYPE 1 ERROR

With a sample size of approximately 480 randomized subjects per zavegepant treatment group and 240 randomized subjects per placebo treatment group, we expect approximately 440 subjects per zavegepant treatment group and 220 subjects per placebo treatment group in the migraine analysis set. Assuming zavegepant provides a 1-day advantage over placebo pooled on the mean change in migraine days per month over the entire DBT Phase (Weeks 1 to 12), common standard deviation of 4.2 days, and a 2-sided  $\alpha = 0.025$  level, then the study has  $\geq 90\%$  power for the primary endpoint. The estimates for the migraine analysis set sample size, mean change in migraine days per month, and standard deviation (SD) are based on observed pooled data from rimegepant study BHV3000-305.

Type 1 error is not applicable. The significance of the primary and secondary endpoints will not be evaluated.

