#### 6.3.1.3 Treatment Group Comparisons

Analyses are based on the migraine analysis set and total pain intensity, unless specified otherwise.

Main Analysis: Migraine Analysis Set

The main analysis of the primary endpoint uses a linear mixed effects model with repeated measures and the following attributes:

- Variables: change from the OP in number of total migraine days per month as the dependent variable; number of total migraine days per month in the OP as a covariate; treatment group, randomization stratum, month (i.e., Months 1 to 3 of the DBT Phase), and the month-bytreatment group interaction as fixed effects.
- Covariance structure for repeated measures accounting for within-subject correlated errors:
   assumed to be homogeneous across treatment groups, and initially specified as unstructured.
   If the model fails to converge or cannot be fit with an unstructured covariance structure, then
   other covariance structures are specified in the following hierarchical order: Toeplitz (which
   has heterogeneous variances and heterogeneous correlations between elements); first-order
   autoregressive with heterogeneous variances; and first-order autoregressive with
   homogeneous variances.
- SE estimation method: Huber-White "sandwich" (refer to the Core SAP).

Note that Protocol Versions 1 to 6 erroneously specify to include subject as a random effect in the model.

The table displays the following model estimates:

- Least-squares mean (LSM) change from OP, SE, and 97.5% CI by month and overall DBT for each treatment group and placebo pooled
- Difference in LSM changes from OP between each zavegepant treatment group and placebo pooled (zavegepanti placebo pooled; *i* = 100 and 200), SE, and 97.5% CI at each month and overall DBT. Results in the overall DBT support the primary objective, results in the last month support secondary objective #2, results in the first month support secondary objective #3, and results in the second month support exploratory objective #1.

See Section 9.3.1 for example SAS code. Model estimates by randomization stratum (yes, no) are presented in the same table, using additional models that exclude randomization stratum as a fixed effect.

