## **Treatment Group Comparisons**

For each pain intensity (total; moderate or severe), the percentages of subjects with  $\geq 50\%$  reduction in the number of migraine days per month are compared between each zavegepant treatment group and placebo pooled using Mantel-Haenszel risk estimation with stratification by randomization stratum (yes, no). Percentages are calculated against the number of subjects in the migraine analysis set.

The table displays the following statistics at each month of the DBT Phase and overall DBT by pain intensity:

- Response rate (i.e., "n/N" and percentage), ASE, and 97.5% CI for each treatment group and placebo pooled
- Stratified percentage difference between each zavegepant treatment group and placebo pooled (zavegepanti placebo pooled; i = 100 and 200), ASE, and 97.5% CI
- Response rate (i.e., "n/N" and percentage), ASE, and 97.5% CI by randomization stratum for each treatment group and placebo pooled
- Percentage difference between each zavegepant treatment group and placebo pooled (zavegepanti placebo pooled; *i* = 100 and 200), ASE, and 97.5% CI by randomization stratum.

Results for the endpoint of  $\geq$  50% reduction of moderate or severe pain intensity in the overall DBT support secondary objective #1. Results for all other endpoints support exploratory objective #2.

Note that Protocol Versions 1 to 6 specify to compare treatment groups using a stratified Cochran-Mantel-Haenszel test, which would produce a chi-square statistic. However, this SAP specifies Mantel-Haenszel risk estimation, which is more appropriate given the estimand is based on a difference in percentages between groups.

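### Does the leftover hierarchical-testing label on the SAP's summary table let unadjusted secondary intervals pass as proof of effect?

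*SAP*

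**What the plan says.** Protocol 9.3.1.3 sets a hierarchy for each dose. The primary endpoint is tested at 0.025 against pooled placebo, and "If the primary endpoint is significant for a dose, then the following secondary efficacy and outcomes research endpoints will be tested hierarchically", each at 0.025, in a fixed order of six.

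The current SAP was cut back after the study was terminated early for business reasons (SAP Section 1). It drops formal testing. Section 5 repeats the power calculation and ends: "Type 1 error is not applicable. The significance of the primary and secondary endpoints will not be evaluated".

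SAP 6.3.2.3 nevertheless keeps a title that refers to hierarchical testing and opens with "An overall summary table of treatment comparisons of primary and secondary endpoints tested hierarchically displays the following statistics". The content that follows is estimation only: least-squares means or response rates, differences from pooled placebo and 97.5% CIs. On sequence it says only "Endpoints are displayed in the order presented in Sections 3.2.1 and 3.2.2".

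SAP 1.1 still carries the research hypothesis that the "oral dose taken daily is safe and effective for the prevention of migraine".

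**The concern.** This table alone brings the primary endpoint and all six efficacy and outcomes-research secondaries together. It keeps three visible features of the protocol's procedure: the hierarchical label, the endpoint order, and a confidence level that matches 0.025 per dose. What it lacks is the gate, the part that protected the secondaries. All 14 between-group intervals are shown alike.

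A reader who took the label at face value could treat a secondary interval that excludes zero as a passed step, even where the same dose's primary interval covers zero. Protocol 9.3.1.3 would have blocked that claim. The SAP nowhere says in so many words that the intervals are per comparison and unadjusted.

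The SAP also notes two other departures from the protocol where they occur. On the random effect it says "Note that Protocol Versions 1 to 6 erroneously specify to include subject as a random effect in the model". On the responder analysis the note begins "Note that Protocol Versions 1 to 6 specify to compare treatment groups" and goes on to explain why a different method is used. Dropping the whole hierarchy gets no such note, so the omission looks like an oversight with consequences.

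**Working it through.** **1. The plan's own figure.** Protocol 9.1 claims at least 90% "power for the primary endpoint with an alpha level of 0.025"; SAP Section 5 adds that this is two-sided.
- Inputs: 440 per dose and 2 × 220 = 440 pooled placebo in the migraine analysis set, difference 1 day, SD 4.2.
- Standard error = 4.2 × √(2/440) = 0.2832. Standardised difference = 1/0.2832 = 3.53.
- Critical value for two-sided 0.025 = 2.2414. Power = Φ(3.53 − 2.2414) = 0.901.

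The figure is reproduced, and nothing in it depends on the wording of 6.3.2.3.

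**2. Number of intervals.** The endpoints are the primary, the 50% responder rate, last-month change, first-month change, acute migraine-specific medication days, MSQ restrictive role function and MIDAS total. Seven endpoints × 2 doses = 14 between-group intervals.

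**3. Size of the misreading.** Suppose neither dose has any effect and each interval is read as a test.
- Upper bound: 14 × 0.025 = 0.35. If all were independent: 1 − 0.975^14 = 0.298.
- Equal groups sharing one placebo group give a correlation of 0.5 between the two dose comparisons. The correlation between endpoints is not in either document, so it is varied here, with the same value for every pair (simulation, normal statistics, limit 2.2414).

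| Assumed between-endpoint correlation | Any of 14 excludes zero | Primary covers zero but a secondary for the same dose excludes it | The same, in favour of zavegepant |
|---|---|---|---|
| 0 | 28% | 24% | 13% |
| 0.3 | 26% | 22% | 11% |
| 0.5 | 22% | 18% | 9% |
| 0.7 | 17% | 13% | 7% |
| 0.9 | 11% | 7% | 3% |

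Under the protocol's gate, a false claim under this null needs a primary interval that excludes zero. For two comparisons correlated at 0.5 that probability is 4.6%, below the bound of 2 × 0.025 = 5%.

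**4. Whether the SAP makes that reading.** Setting the sections side by side:
- *Decision rule.* Section 5 says significance is not evaluated, for primary and secondary endpoints alike. The model and responder tables (6.3.1.3, 6.3.2.1, 6.3.2.2, 6.5.1, 6.5.2) and the summary table (6.3.2.3) specify no p-value, and 6.3.2.3 has no gate and no criterion for success.
- *Confidence level.* The 97.5% level also applies to descriptive means of migraine days (6.3.1.2), descriptive means of medication days (6.3.2.2), liver-test elevation tables (6.4.2.2) and all outcomes-research intervals (6.5). It is a general convention of this SAP and does not mark a step in a test sequence.
- *Order.* The display order is that of the objectives in SAP 3.2.1 and 3.2.2. It would be the same had no hierarchy existed.
- *Hypothesis.* SAP 1.1 repeats Protocol 1.4.4. An estimation-only report leaves it without a formal test, which is what the decision in Section 5 means.
- *Origin of the wording.* The revision history for SAP Version 8 records that text on p-values and hierarchical testing was taken out of 6.3.2.3. The title and the opening phrase were missed.

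The rates in step 3 are therefore those of a procedure the SAP disclaims. They are not operating characteristics of the planned analysis.

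**The case for a change.** The strongest case for acting is that Section 5 says what will not be done without saying what the intervals are. It does not call them descriptive, per comparison or unadjusted, while several SAP sections say that results support the efficacy objectives. A report author who followed 6.3.2.3 to the letter could print a heading that promises controlled testing over a table that has none. Correcting it would cost a few words, and dropping the hierarchy is a larger departure from the protocol than the two the SAP does annotate.

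Three parts of this stand. The label contradicts Section 5. An explicit statement that the intervals are unadjusted is absent from this SAP (the Core SAP could not be checked). There is no cross-reference to Protocol 9.3.1.3.

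The rest does not carry. It is not true that no rule governs the table: if significance is not evaluated, an interval that excludes zero is not a finding of significance. The departure is declared openly in Section 5, and Section 1 gives the background; the two annotated departures are of another kind, each replacing a method the SAP regards as mistaken or less suitable. Table templates sit in a separate mock document (SAP 6.1.1), so it is not known that the section title is the printed table title or that a footnote is lacking.

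Nor would it help to single out the two primary intervals as able to carry an efficacy conclusion. Section 5 removes significance evaluation for the primary endpoint as well, so the number of rows that support a formal claim is zero now, and such a rule would bring back the inference the SAP gave up.

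**Conclusion.** The concern rests on a clerical remnant. The title and opening phrase of SAP 6.3.2.3 are out of step with Section 5, and a careful analyst would settle the matter from Section 5: report the estimates and 97.5% CIs and claim no significance. With or without the label, the plan yields the same 14 between-group differences, the same intervals, the same 90% design power and the same absence of significance claims.

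The 17% to 26% range holds for assumed between-endpoint correlations of 0.7 down to 0.3 when neither dose has an effect. It measures how often a reader who ignored Section 5 could be misled, and it is not an error rate of the analysis. Deleting the remnant words, calling the intervals unadjusted and citing Protocol 9.3.1.3 would be harmless tidying if the document were reissued for another reason. None of it alters what is analysed or concluded, so no change to the plan is called for.

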## 6.3.3 Exploratory Efficacy Endpoints

## 6.3.3.1 Acute Migraine Medication Days per Month in the DBT Phase

Acute migraine medication days per month are assessed analogously to acute migraine-specific medication days per month (see Section 6.3.2.2).

An acute migraine medication day is defined in Section 9.2.3.

Analyses are based on the migraine analysis set with eDiary efficacy data dates in the on-DBT efficacy analysis period.

The number of acute migraine medication days per month in the DBT Phase are prorated to 28 days.

#### **Descriptive Analyses**

The table of the number of acute migraine medication days per month in the DBT analysis period is provided, and has the same format as the one in Section 6.3.2.2.

#### 6.3.4 Pharmacokinetics

Sparse PK sampling is performed at Week 4 and 8 at predose and approximately 1 hour postdose. PK last meal/snack date/times, collection date/times, and last IP dosing date/times are based on the PK CRF. Plasma zavegepant concentrations and collection date/times are from the external source Syneos Health.

The by-subject listing of plasma zavegepant concentrations is provided for the DBT efficacy analysis set, which includes analysis visit, analysis time point, PK collection date/time, last IP dose collection date/time, last meal/snack date/time before and after the predose sample concentration, study days corresponding to aforementioned date/times, and concentration. BLQ values are displayed as "BLQ". A footnote specifies the lower limit of quantification (LLOQ) of 0.04 ng/mL and the upper limit of quantification (ULOQ) of 50.00 ng/mL.

First, PK samples are slotted into analysis visit windows defined in Section 7.3 according to PK collection date. Next, PK samples are slotted into analysis time point windows within analysis visit windows according to PK collection date/time as follows:

- Predose: last PK sample with collection date/time before the last IP dose collection date/time
- 1 hour postdose: first PK sample with collection date/time after the last IP dose collection date/time.

CRF and external PK data are merged by PK collection date/time, where the external data take precedence.

## 6.4 Safety

Safety parameters include the following: deaths; AEs; laboratory tests; vital signs; physical measurements; electrocardiograms (ECGs); and Columbia-Suicidality Severity Rating Scale (C-SSRS.

Tables of safety endpoints are provided according to safety analysis period and analysis set as follows:

- On-DBT for the DBT safety analysis set by treatment group, zavegepant pooled, and placebo pooled
- Post-DBT pre-OL zavegepant for the interim safety analysis set by treatment group, zavegepant pooled, placebo pooled, and overall
- On-OL zavegepant for the OL zavegepant safety analysis set by OL zavegepant dose and overall
- On-DB or OL zavegepant for the DB or OL zavegepant safety analysis set by DB or OL zavegepant dose and overall
- Follow-up for the follow-up safety analysis set by treatment group/OL zavegepant status and overall.

Treatment group is as-treated according to Section 6.1.1.1.

Measurements are slotted into analysis periods and analysis visits using the following steps:

- 1) Measurements are slotted into the pretreatment, on-treatment safety, and follow-up safety analysis periods.
- 2) Measurements are slotted into analysis visits in the analysis periods listed in the previous step (see Table 5). This does not apply to AEs.
- 3) Measurements in the on-treatment safety analysis period are slotted further into the on-DBT, post-DBT pre-OL zavegepant, and on-OL zavegepant safety analysis periods.

Refer also to the Core SAP for details about measurement slotting. See Sections 6.2.5, 7.2 and 7.3 for definitions of baseline, analysis periods, and analysis visit windows, respectively.

